#### 4.4 Study Design

This study is an observational, prospective, multicentre study to assess the effectiveness of conservative and invasive treatments of patients with CVD in Belgium. The inclusion period of the study will last 6 months. Patients will be followed until 2 years after inclusion into the study. The study is expected to start in Jan-2024 and be completed by Jul-2026.

During the inclusion period, after confirmation of eligibility, patients with CVD diagnosed by the GP and looking for a treatment will be invited to participate in the study. About 120 GPs will be included in the study.

#### **4.4.1 Physician recruitment**

GPs will be selected throughout Belgium, based on their experience of clinical trials and the number of patients they may recruit in the study. The selection and contracting of the GPs will be organized by Keyrus Life Science. Participating GPs will sign an agreement contract and will receive an electronic Case Report Form (eCRF) completion fee. All participating GPs are expected to have undergone accredited training in CVD and CEAP, rVCS and CIVIQ-20 scoring before the site activation.

#### **4.4.2 Study setting**

The GP examines the patient and makes the diagnosis of CVD, based on clinical signs and symptoms. Patients who receive a diagnosis of CVD according to international guidelines who require conservative or invasive treatment can be included in the study. Duplex ultrasound or any other specific examination is not required to make the diagnosis, but could be done if needed according to routine clinical practice and recommendations. Each participating GP (120 GPs) will select approximately between 10 and 15 patients with CVD.

During the inclusion visit (V0), a treatment strategy will be proposed to the patient with confirmed CVD by the GP. The treatment can be conservative or invasive, depending on the severity of the disease. Patients awaiting invasive treatment may receive conservative treatment to alleviate symptoms. The choice of treatment modality is left to the discretion of the treating physician, in agreement with the patient and according to local policies. As this is an observational study, there will be no interference in the choice of treatment, and no restrictions will be imposed.

Commonly proposed conservative treatment options include compression therapy, and oral or topical venoactive drugs. If the GP decides that the patient needs an invasive treatment, then the patient will be referred to a venous centre. The specialist to whom the patient is referred, chooses the type of invasive treatment, as done in standard clinical care. The specialist may also prescribe conservative treatment to the patient, either while awaiting invasive treatment or in case invasive treatment is not deemed necessary.

[figure not shown]
Patients and their GP may decide to switch at any time between conservative treatments or to undergo an intervention as secondary/add-on treatment to conservative treatment.

Baseline data will be collected by the GP on the day of the V0. Follow-up visits, which are expected to take place within the scope of routine clinical practice, will be organized by the GP at defined timepoints after the V0: at 6 weeks, 12 weeks, 6 months, 12 months and 24 months of follow-up (V1-V5).

A delay between referral to the venous centre during the V0 and the day of invasive treatment is anticipated. To allow assessment of the primary study objective, GPs will be asked to invite the patients for a follow-up visit 12 weeks after the invasive treatment took place (V-i), provided that it falls within the scope of routine medical practice in terms of visit frequency.

Due to the real-world setting, patients might not be assessed exactly at the proposed weeks/months. Therefore, some visits may not take place if they are not within the scope of regular medical practice. Additionally, a time range around the visits will be allowed. The frequency of follow-up visits is upon the discretion of the treating physicians.

**4.5 Study diagram**

**Figure 1. Study diagram**

AEs: Adverse Events, CEAP: Clinical Etiological Anatomic Pathophysiologic classification, CIVIQ-20: Chronic Venous Insufficiency Quality of life questionnaire, CVD: Chronic Venous Disease, GP: General Practitioner, rVCSS: revised Venous Clinical Severity Score.

**4.6 Study Flowchart**

**Table 1. Schedule of assessments**

| Visits                       | V0                      | V1     | V2      | V3      | V4       | V5       | V-i a                  |
|------------------------------|-------------------------|--------|---------|---------|----------|----------|-----------------------------------|
|                              | Inclusion visit (Day 0) | Week 6 | Week 12 | Month 6 | Month 12 | Month 24 | 12 weeks after invasive treatment |
| Informed consent             | X                       |        |         |         |          |          |                                   |
| Inclusion/exclusion criteria | X                       |        |         |         |          |          |                                   |

|  |                |   |   |   |   |   |   |
|--|----------------|---|---|---|---|---|---|
| Patient characteristics b   | X              |   |   |   |   |   |   |
| Risk factors   | X              | X | X | X | X | X | X |
| Treatment characteristics
(type/day of treatment
initiation)                                 | X c | X | X | X | X | X | X |
| Conservative treatment
compliance   |                | X | X | X | X | X | X |
| Concomitant treatment  | X              | X | X | X | X | X | X |
| Treatment changed since
last visit/intervention as
secondary treatment or
re-intervention |                | X | X | X | X | X | X |
| CIVIQ-20 d  | X              | X | X | X | X | X | X |
| CEAP   | X              | X | X | X | X | X | X |
| rVCSS  | X              | X | X | X | X | X | X |
| Symptomatology d  | X              | X | X | X | X | X | X |
| Satisfaction d  |                | X | X | X | X | X | X |
| AEs  |                | X | X | X | X | X | X |
| Study discontinuation  |                | X | X | X | X | X | X |

AEs: Adverse Events, CEAP: Clinical Etiological Anatomic Pathophysiologic classification, CIVIQ-20: Chronic Venous Insufficiency Quality of life questionnaire, V: Visit, rVCSS: revised Venous Clinical Severity Score

a If the V-i overlaps with another visit (V1-V5) then it will replace this visit.

b Patient characteristics include demographics, type of occupational activity, clinical characteristics, history of CVD, treatment history, specific comorbidities.

c Date of treatment initiation for the conservative group and date of intervention in the invasive group will be collected retrospectively during a subsequent visit.

d The CIVIQ-20 questionnaire, symptomatology visual analogue scale and satisfaction score will be completed by the patients themselves.

## 5. Selection and withdrawal of subjects

This observational study conducted in real-life setting will include patients with CVD diagnosed by the GP during the VO. To ensure representativity, investigators will be asked to select consecutive patients whenever possible, and based on the inclusion and exclusion criteria. Patients will be managed and treated according to the usual practice.

### 5.1 Inclusion criteria

Patients must meet all the following criteria to be included in the study:

- Patient visiting a GP with complaints related to CVD,
- Patient aged  $\geq 18$  years old at inclusion,
- Patient receiving the diagnosis of CVD from the GP during the VO, according to international guidelines and made on a clinical basis,
- Patient requiring and agreeing to receive conservative or invasive treatment,
- French or Dutch speaking patient,
- Patient signed informed consent and agrees to take part in the study and follow-up.

### 5.2 Exclusion criteria

Patients meeting any of the following criteria will not be eligible for inclusion in the study:

- Patient with coagulation disorders such as thrombophilia and/or taking anticoagulation drugs,
- Pregnant or breastfeeding patient,
- Patient with severe Peripheral Arterial Occlusive Disease (POAD), with Ankle Brachial Index (ABI)  $< 0.8$ ,
- Patient with malignancy,
- Patient with neurological disorder or dementia,
- Patient taking regular treatment for CVD 3 months prior to inclusion (except painkillers or anti-inflammatory drugs if taken for reasons other than CVD),
- Patient in any other clinical study for any pharmaceutical product within 4 weeks preceding study inclusion,
- Patient with any comorbidity or situation preventing a follow-up of 2 years.

### 5.3 Expected duration of study

The end of the study is defined as 2 years after the first visit of the last patient included (Last Patient First Visit [LPFV]). The total duration of the study will be 2 years and half (6 months of inclusion + 2 years of follow-up).

Patients have the right to withdraw from the study at any time and for any reason without prejudice for their future medical care. Patients can withdraw their consent without the need to justify their decision. In case of consent withdrawal, data collection will stop from the date of consent withdrawal.

Patients will be considered lost to follow-up if the investigator is not able to contact them despite multiple attempts. In case of study withdrawal, the reason for discontinuation should be recorded. The sponsor has the right to prematurely discontinue the study if the decision is justified.

## 6. Study Variables

### 6.1 By visit

During the **V0**, the patient eligibility will be assessed (inclusion/exclusion criteria, informed consent) and several variables will be collected:

- Patient characteristics: demographics (age, sex), type of occupational activity, clinical characteristics (primary/recurrent disease), personal history of CVD, family history of CVD, treatment history, specific comorbidities (diabetes, dysthyroidism, cardiovascular disease)
- Risk factors (weight, height, Body Mass Index [BMI], physical activity, smoking, pregnancy).
- Treatment characteristics: initial prescription/referral from GP, concomitant treatment, date of treatment initiation for the conservative group and date/type of intervention in the invasive group. Dates will be collected retrospectively during a subsequent visit.
- Baseline scores for CIVIQ-20, CEAP, rVCSS, and symptomatology will be collected.

Follow-up visits will be organized by the GP at defined timepoints after the V0: at 6 weeks, 12 weeks, 6 months, 12 months and 24 months of follow-up (V1-V5). Due to the real-world setting, patients might not be assessed exactly at the proposed weeks/months. Therefore, some visits may not take place if they are not within the scope of regular medical practice. Additionally, a time range around the visits will be allowed. The frequency of follow-up visits is upon the discretion of the treating physicians.

A delay between referral to the venous centre during the V0 and the day of invasive treatment is anticipated. To allow assessment of the primary study objective, GPs will be asked to invite the patients for a follow-up visit 12 weeks after the invasive treatment took place (V-i), provided that it falls within the scope of routine medical practice in terms of visit frequency. If the V-i overlaps with another visit (V1-V5) then it will replace this visit. If more than one measurement is available, the value closest to the timepoint assessed will be considered. If two values are equally close, i.e., one value before and one value after, the first one will be taken.

During V1-V5 and V-i the following variables will be collected, if available:

- Risk factors (see V0)
- Treatment characteristics:
  - o was the prescribed treatment initiated, type of treatment (conservative: venoactive drugs, compression, or combination; invasive: sclerotherapy, foam sclerotherapy, surgery, thermal ablation (laser or radiofrequency), non-thermal ablation, venous stenting)

- concomitant treatment
- compliance with conservative treatment, as reported by the patient
- change of treatment since the last visit, intervention as secondary/add-on treatment (in case of conservative treatment; if yes: date), re-intervention (in case of invasive treatment; if yes: date)
- CVD-related QoL: CIVIQ-20 score
- Clinical features: CEAP score
- Disease severity: rVCS
- Patient-reported symptomatology score
- Patient-reported satisfaction score
- AEs: AE type, start date, end date, grade, outcome, lead to drug dose reduction or drug discontinuation (yes/no; only in case of conservative treatment)
- Study discontinuation

The detailed list of variables that will be collected during the conduct of the study will be provided in the eCRF and in the Statistical Analysis Plan (SAP).

## 6.2 Laboratory tests

Not applicable.

## 6.3 Other investigations

Not applicable.

# 7. Assessment of effectiveness

The primary outcome is the patients' QoL, related to the CVD. The CIVIQ-20 (Chronic Venous Insufficiency quality of life Questionnaire) considers CVD as a whole (Launois 2010, Vuylsteke 2015). It is a reliable, valid, and sensitive instrument applicable to international studies of patients with CVD. The maximal score is 100, with a high score corresponding to lower patient comfort. In order to calculate the GIS, the difference between the final score and the minimum possible score is to be divided by the difference between the theoretical maximum and minimum scores ( $100-20=80$ ), multiplied by 100.

For the primary endpoint, the CIVIQ-20 score will be collected at V0, and at V2 (12-weeks after V0) for the conservative treatment group and at V-i (12 weeks after the day of invasive treatment) for the invasive treatment group.

The secondary outcomes are:

1. Patient characteristics at V0 as described in [Section 6.1 By visit](#).
2. Treatment characteristics as described [Section 6.1 By visit](#).
3. The **CIVIQ-20** GIS, as described above for the primary outcome.

4. The **CEAP** classification, which is the worldwide standard for describing the clinical features of CVD. In this survey, we only use the C-classification. It is a scale from 0 (C0) to 6 (C6), with a higher score representing more severe disease. However, as a descriptive instrument, the CEAP classification responds poorly to change.
5. The **VCSS** was developed in 2000 and adapted in 2010 (r-VCSS) ([Rutherford 2000](#), [Vasquez 2010](#)). The r-VCSS is an evaluative instrument that is responsive to changes in disease severity over time and in response to treatment. It includes 10 items, each scored on a severity scale from 0 to 3 (maximal score: 30; a higher score representing more severe disease). It enables longitudinal outcomes assessment.
6. Patients will evaluate CVD related **symptoms** using a Visual Analogue Scale (VAS) varying from 0 to 10. Symptoms include: having heavy legs, having pain in the legs, sensation of swelling, having night cramps, itching [leg], sensation of burning, sensation of pins and needles, restless legs. This list of symptoms has been validated by the SYM VEIN consensus statement ([Perrin 2016](#)). The final list of symptoms will be defined in the eCRF.
7. The patient **satisfaction** rate: the patients provide a score from 0 (not satisfied) to 10 (very satisfied) regarding the result of the treatment offered for their CVD.
8. The CIVIQ-20, CEAP, rVCSS, symptomatology and satisfaction scores, as detailed above, in patients who received an intervention as secondary/add-on treatment to conservative treatment.
9. Assessment of AEs will be described in [Section 8](#).

All of these outcomes, except for treatment failure characteristics, satisfaction, and AEs, will be measured at V0. All outcome measures will be collected V1-V5 (6 weeks, 12 weeks, 6 months, 12 months and 24 months after the V0) and V-i (12 weeks after the day of invasive treatment).

## 8. Assessment of safety

### 8.1 Specification, timing and recording of safety parameters

According to the International Conference on Harmonisation (ICH), an **AE** is any untoward medical occurrence in a subject or clinical investigation subject administered a pharmaceutical product and which does not necessarily have a causal relationship with this treatment. An AE can therefore be any unfavourable and unintended sign (including an abnormal laboratory finding), symptom or disease temporally associated with the use of a medicinal (investigational) product, whether or not related to the medicinal (investigational) product. Worsening of a pre-existing condition during the study must also be recorded as an AE.

A Treatment Emergent Adverse Event (**TEAE**) is defined as any event not present prior to the initiation of the treatments or any event already present that worsens in either intensity or frequency following exposure to the treatments.

A Serious Adverse Event (**SAE**) is defined as any untoward medical occurrence that:

- Results in death,
- Is life-threatening (the term 'life-threatening' refers to an event in which the subject was at risk of death at the time of the event; it does not refer to an event which hypothetically might have caused death if it were more severe),
- Requires inpatient hospitalisation or prolongation of existing hospitalisation,
- Results in persistent or significant disability or incapacity,
- Is a congenital anomaly or birth defect.

Pharmacovigilance data include any unintended or adverse event associated with the use of a medicinal product in humans, whether or not considered drug related, including the following special situations (situations where no AE occurred but information needs to be collected):

- Exposure during pregnancy (maternal and/or transmission of a medicinal product via semen following paternal exposure) or breastfeeding,
- Overdose, abuse, misuse, off label use, medication error, occupational exposure,
- Drug-drug or drug-food interactions,
- Any suspected transmission via a medicinal product of an infectious agent,
- Unintended therapeutic benefit,
- Lack of efficacy.

AEs and special situations will be assessed during each follow-up visit and recorded in the eCRF.

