## 4. Study objectives and Design

### 4.1 Study objectives

The **primary objective** is to assess the evolution of the QoL after 12 weeks for patients with CVD who underwent conservative or invasive treatment.

The **secondary objectives** are:

1. To describe patient characteristics by treatment group, including demographic characteristics, clinical characteristics and specific comorbidities at the inclusion visit (V0), and risk factors and treatment characteristics per visit.
2. To estimate the proportion of patients who received an intervention as secondary/add-on treatment to conservative treatment or who received a re-intervention, and the time to secondary/add-on intervention or re-intervention.
3. To assess the evolution of the QoL over time by treatment.
4. To assess the evolution of the clinical part of the Clinical Etiological Anatomic Pathophysiologic (CEAP) classification over time by treatment.
5. To assess the evolution of patient’s signs through physician-assessed revised Venous Clinical Severity Score (rVCSS) over time by treatment.
6. To assess the evolution of patient’s assessment of symptom severity over time by treatment.
7. To assess the evolution of patient satisfaction over time by treatment.

8. To assess QoL, signs, symptoms and patient satisfaction of patients who received an intervention as secondary/add-on treatment to conservative treatment.
9. To assess the safety of treatments in patients with CVD.

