#### 4.3 Secondary endpoints

The secondary endpoints are:

1. Description of patient characteristics by treatment group at V0 (demographics, clinical characteristics, history of CVD, treatment history, specific comorbidities) and description of risk factors and treatment characteristics per visit (type of treatment [initial referral from General Practitioner (GP) and whether they actually received the treatment], concomitant treatment, compliance with conservative treatment).
2. Proportion of patients who received an intervention as secondary/add-on treatment to conservative treatment (in the conservative treatment group). Proportion of patients who received a re-intervention (in the invasive treatment group) and number of re-interventions. Time to secondary/add-on intervention or re-intervention.
3. The change in the GIS of CIVIQ-20 over time from V0 to each follow-up visit.
4. The change in the clinical part of the CEAP classification over time from V0 to each follow-up visit.
5. The change in the rVCSS over time from V0 to each follow-up visit.
6. The change in the symptomatology over time from V0 to each follow-up visit.
7. The change in satisfaction score over time from V1 to each follow-up visit.
8. The change in CIVIQ-20, CEAP, rVCSS, symptomatology and satisfaction scores in patients who received an intervention as secondary/add-on treatment to conservative treatment.
9. Number and proportion of patients with Adverse Events (AEs).

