## **8.2 Procedures for recording and reporting adverse events (AE)**

The investigator must record all AEs presented or reported by the patient in the AE section of the eCRF. The start date, the actions taken (concomitant treatments, discontinuation of treatment, dose change, premature withdrawal, none, other) and the outcome (ongoing, not recovered, recovered with / without sequelae, death, unknown) must all be recorded and the investigator must assess the event in terms of seriousness, severity and relationship to the conservative or invasive treatments studied.

When possible, signs and symptoms should be reported as a diagnosis i.e. the investigator should avoid reporting only the signs and symptoms. If there is no medical diagnosis and the signs and symptoms have to be reported, the investigator should record a separate AE for each sign and symptom.

The severity of the AEs will be judged by the investigator(s) and recorded as follows:

- Mild: discomfort noticed but no disruption of normal daily activity,
- Moderate: discomfort sufficient to reduce or affect daily activity,
- Severe: inability to work or perform normal daily activity.

The relationship of the AE to the conservative or invasive treatments will be judged by the investigator(s) and recorded as follows:

- Related: there is reasonable causal relationship between the treatment and the AE,
- Unrelated: there is no reasonable causal relationship between the treatment and the AE.

The proposed study is observational research that makes use of data collected as part of routine care and does not involve alteration of clinical care. Investigators should follow usual reporting rules to fulfil Belgian pharmacovigilance reporting.

Safety evaluations for this study are limited to the specified safety outcomes stated in [Section 8.1](#).

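### The Section 8.1 AE definition uses drug-trial wording, so read literally it omits new, non-serious complications of procedures or compression in patients given no drug, in conflict with objective 9 and Section 8.2

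*Protocol*

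**What the plan says.** Section 8.1 of the protocol defines an AE as "any untoward medical occurrence in a subject or clinical investigation subject administered a pharmaceutical product". Its next sentence describes an unfavourable sign, "symptom or disease temporally associated with the use of a medicinal (investigational) product". Three other parts of 8.1 carry no such limit: the treatment-emergent AE (TEAE) definition, which refers to the treatments; the opening of the serious AE (SAE) definition; and the instruction to record as an AE any deterioration of a condition the patient already had.

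Section 8.2 tells the investigator to record all AEs and adds that "the investigator must assess the event in terms of seriousness, severity and relationship to the conservative or invasive treatments studied". It closes: "Safety evaluations for this study are limited to the specified safety outcomes stated in" Section 8.1.

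The ninth objective in Section 4.1 is "To assess the safety of treatments in patients with CVD". The matching endpoint in Section 4.3 is "Number and proportion of patients with Adverse Events (AEs"). Section 6.1 lists the treatments to be recorded. The conservative ones are venoactive drugs, compression or both; the others are "invasive: sclerotherapy, foam sclerotherapy, surgery, thermal ablation (laser or radiofrequency), non-thermal ablation, venous stenting". For safety, the same section lists "AEs: AE type, start date, end date, grade, outcome, lead to drug dose reduction or drug discontinuation (yes/no; only in case of conservative treatment").

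**The concern.** The definition was written for studies in which everyone receives a medicine. In this study some patients may have surgery, thermal ablation, a stent or compression stockings and no drug. Section 4.4.2 makes drug or other conservative treatment while awaiting an intervention optional, so drug exposure cannot be taken for granted in the invasive group.

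The ninth endpoint is at stake. Section 9.3.3 has the secondary endpoints analysed overall and by treatment group, so AE proportions for the conservative and invasive groups will be presented side by side. If some GPs apply 8.1 to the letter and others follow the spirit of 8.2, capture differs by treatment as well as by site. This is settled when the event is or is not entered; it cannot be repaired at analysis.

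**Working it through.** There is no figure in the plan to reproduce. The check sets the passages against each other.

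1. **Who meets the first AE sentence (8.1)?** Anyone given a pharmaceutical product, whatever caused the event. The sentence does not say which product, so a patient on a venoactive drug before an intervention qualifies, even for a surgical complication.

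2. **Which events meet the second sentence (8.1)?** Those that follow the use of a medicinal product in time. A patient with no drug exposure has none.

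3. **Which studied treatments can leave a patient without a drug (6.1)?** Clearly surgery, thermal ablation, stenting and compression alone. The protocol does not describe the agents used in sclerotherapy or non-thermal ablation, so the argument does not rest on those.

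4. **What does 8.1 recover by other wording?** Serious events, through the SAE definition, and deterioration of existing conditions. The TEAE definition would also cover new events after any treatment, but the duty in 8.2 and the endpoint in 4.3 are both expressed in AEs, not TEAEs.

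5. **What remains outside?** New, non-serious events in patients with no drug exposure. Section 3 itself names pain, paraesthesia and ecchymosis as usual side-effects after invasive treatment, so this category is relevant.

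6. **Does 8.2 close the gap?** Not by its terms. It shows that procedural events are wanted, but it uses the term defined in 8.1 and then refers safety evaluation back to 8.1.

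On size, let q be the true proportion of patients in a group with at least one AE, s the share of those patients whose events all lie in the category of step 5, and f the fraction of that share seen by GPs who apply 8.1 literally. The recorded proportion is then

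q × (1 − s × f).

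The documents give none of q, s or f. With s and f each free between 0 and 1, the result can lie anywhere from q (no loss) down to q × (1 − s) (when f = 1). For patients who took a drug, s = 0 on the first sentence of the definition, so any loss falls on the others.

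**The case against.** The best reply is that no sensible GP would read 8.1 this way. Section 8.2 requires all AEs to be recorded and judged against invasive treatment. Table 1 schedules AE collection at every follow-up visit, including the visit 12 weeks after an intervention, with no drug condition. The qualifier on the drug-action field in 6.1 itself presupposes AEs in patients without conservative treatment. This stands as evidence of intent. It limits the point to an inconsistency, but it does not change the definition.

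Three stronger readings are tempting, and the documents do not support them.

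- A reader might infer that a patient treated only by surgery or compression can have no recordable event. The SAE wording and the rule on existing conditions contradict that.
- A reader might infer that the AE endpoint will be biased in favour of procedures and compression. Under-capture is possible, not shown. AEs are only described, and no between-group AE test is planned.
- A reader might infer from 6.1 that seriousness, relationship and actions taken will not be collected, or that drug actions are lost in invasive-group patients who take a drug while waiting. Section 8.2 requires all three items for every AE, and 6.1 leaves the detailed variable list to the eCRF and SAP. The qualifier in 6.1 refers to conservative treatment, not to the conservative group.

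**Conclusion.** The inconsistency is real and narrow. Taken literally, 8.1 leaves out new, non-serious complications of surgery, ablation, stenting or compression in patients without drug exposure. That conflicts with the ninth objective, with the TEAE definition in the same section, and with the relationship assessment in 8.2. Endpoint 9 could be under-counted in those patients if some GPs follow the definition to the letter. Whether and how often that would happen cannot be derived from the protocol, so no magnitude is claimed. The primary endpoint is unaffected. The conclusion assumes only that some patients receive no drug, which the listed treatments and the optional nature of interim treatment allow. Correction is worthwhile because it is nearly free and has to be in place while events are being recorded.

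**What to change.** In 8.1, replace the two product-based sentences with a definition tied to study participation: an AE is any unfavourable medical event arising during follow-up, from V0 and including time spent waiting for an intervention, in a patient included in the study, whether or not related to any conservative (drug or compression) or invasive treatment for CVD. Starting at V0 makes clear that events in a patient still awaiting treatment count; the TEAE definition then picks out those that begin or worsen after treatment.

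As a consistency edit, have the AE entry in 6.1 refer to the items required by 8.2: seriousness, relationship and actions taken.

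The cost is protocol wording and, where needed, alignment of the eCRF fields with what 8.2 already demands. The downside is slightly more AE entries per GP. No treatment rule is affected.
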